2. INTRODUCTION

2.1. Background

Adrabetadex (VTS-270) is a specific and well-characterized mixture of HP- β -CD, a cyclic oligosaccharide with a distinctive truncated cone configuration containing 7-cyclo- α -(1,4)-anhydroglucose units with hydroxypropyl groups randomly substituted onto the C-2, C-3, and C-5 positions of the molecule. The level of hydroxypropylation in adrabetadex is strictly controlled during manufacturing, resulting in a drug with a tightly controlled degree of substitution and a defined fingerprint of the different species present in the mixture. This unique fingerprint distinguishes adrabetadex from all other commercially available HP- β -CDs.

The therapeutic potential of HP- β -CD was discovered in 2009 when HP- β -CD, injected systemically to Niemann-Pick Type C1 (NPC1) $^{+/-}$ mice beginning at either postnatal Day 7 or 21 and continuing every other day, delayed onset of clinical symptoms, reduced intraneuronal cholesterol and glycosphingolipid storage, reduced markers of neurodegeneration, and increased animal survival ([Davidson, 2009](#)). HP- β -CD enters cells by the endocytic pathway and is delivered to the late endosomal/lysosomal storage organelles where unesterified cholesterol accumulates in NPC1 deficiency. HP- β -CD replaces the function of NPC1 protein and promotes transport of the accumulated unesterified cholesterol to the endoplasmic reticulum for esterification by acetyl coenzyme A:acyl transferase and subsequent efflux ([Abi, 2009](#); [Rosenbaum, 2011](#)). While the precise mechanism of HP- β -CD action to bypass or replace NPC1 function is not defined, HP- β -CD normalizes intracellular cholesterol trafficking by binding the hydrophobic moieties of cholesterol and other lipids.

A detailed description of the chemistry, pharmacology, efficacy, and safety of adrabetadex is provided in the Investigator's Brochure.

2.2. Study Rationale

At present, there are no therapies approved for use in the United States (US) for subjects with NPC1 disease. Miglustat (Zavesca \circledR), an imino sugar, has been approved for the treatment of subjects with NPC1 disease in many countries outside the US, including the European Union; off-label use in the United States (US) is available. The efficacy of Miglustat is modest at best, and development of effective treatments for NPC1 is required to address the significant unmet need for this fatal disease.

This study is designed to enable subjects who have completed the treatment phase of Study VTS301 with an assessment by the treating principal investigator in Study VTS301 of continued benefit to have continued treatment with adrabetadex and consensus of the principal investigator (PI) in the current study. A completer is defined as a subject who has completed Visit 27/Week 52 or completed at least through Visit 13/Week 24 and required rescue option,

and is continuing in Part C of Study VTS301. Subjects will enter this study at the same dose and regimen they were taking upon exiting Study VTS301.

2.3. Assessment of Potential Benefits and Risks

NPC1 is a fatal disorder with both systemic and central nervous system signs and symptoms. Although age of onset varies, subjects typically develop progressive cerebellar dysfunction, hearing impairment, and motor and cognitive deterioration with death typically occurring during adolescence.

Ototoxicity, an expected AE based on the feline model, was observed in Study 13-CH-0001 at doses of 200 mg and higher, as assessed by tonometric audiometry. The clinical assessment of drug-related ototoxicity is confounded by disease related ototoxicity occurring as the course of Niemann-Pick Type C (NPC) progresses. Regardless, data in murine and feline NPC models show a dose-dependent hearing impairment with adrabetadex treatment, with variable susceptibility as is common in otopathology, suggesting that a number of external factors may influence the ototoxic properties of adrabetadex ([Davidson, 2009](#); [Ory, 2017](#); [Ward, 2010](#)).

The degree of recovery from ototoxicity in adrabetadex treated subjects has not been clearly documented due to limited clinical data. Pure-tone audiometry has indicated partial, and in some cases, complete recovery. Therefore, some degree of ototoxicity with uncertain reversibility may occur in subjects receiving adrabetadex. The mechanism of ototoxicity is not fully understood; however, based on preclinical and clinical data, it is possible that higher doses or longer duration of dosing may result in further hearing impairments. It should be noted that subjects with decreased hearing may benefit from use of assisted hearing devices such as hearing aids or cochlear implants. The overall preclinical and clinical data suggest that there is risk of hearing impairment associated with the administration of adrabetadex. Animal data suggest that the potential mechanism of adrabetadex-induced hearing impairment is a loss of outer hair cells in the cochlea of the inner ear, which amplify low-level sounds reaching the cochlea([Crumling, 2017](#); [Ward, 2010](#)). Moreover, in a clinical setting, fatigue-like symptoms, balance disorders and pyrexia were observed in the Study VTS301 and Study 13-CH-001 and may be associated with the administration of adrabetadex.

Although there are case reports from a few expert treating physicians indicating a potential benefit of adrabetadex in NPC patients treated over a period of time, a comprehensive evaluation of all available clinical data shows no clear evidence of benefit of adrabetadex in the treatment of neurologic symptoms of NPC. In view of established risks of treatment with adrabetadex, Mallinckrodt concludes that the benefit / risk balance is negative.

Effective 20 January 2021, Mallinckrodt is recommending that treatment with adrabetadex be discontinued as soon as possible with appropriate clinician oversight.

In recognition of the complexity of patient care, Mallinckrodt will make adrabetadex available for up to 9 months to allow time for the physician and patient/family to develop a transition plan. Continued treatment with adrabetadex is contingent upon a discussion between the treating

physician and patient/family and re-consent. Likewise, continuation of treatment is also contingent upon approval by the respective Institutional Review Board / Ethics Committee and health authority.

More detailed information about the known and expected benefits, risks, and reasonably expected AEs can be found in the Investigator's Brochure.

3. OBJECTIVES AND ENDPOINTS

3.1. Primary Objective(s)/Endpoint(s)

Primary Objective	Endpoint
To evaluate the long-term safety and tolerability of adrabetadex in subjects transitioning from Study VTS301.	
Primary baseline values are collected from the first assessment gathered in the Study VTS301, which is before the first dose of adrabetadex in Study VTS301.
 
Baseline values of the current study at Visit 1 are from evaluations gathered within the study period of Study VTS302 to account for newer raters in the study. These values will reflect evaluations by the Primary Investigator of the current study, performed within the study sites described in the Overall Design.
 
Endpoints will be assessed at Weeks 26, 52, 78, 104, 130, and/or 156 (end of study) (Note: The last possible date of treatment is 20 October 2021. A follow-up visit will be conducted after that date.)
 
Summary of general safety profile, including AEs (serious and nonserious), vital signs, change in annual weight, and laboratory parameters.

3.2. Secondary Objectives/Endpoints

There are no secondary objectives for this study.

3.3. Exploratory Objectives/Endpoints

There are no exploratory objectives for this study.

4. STUDY DESIGN

4.1. Overall Design

This is a multicenter, multinational, open-label study of adrabetadex, with intrathecal (IT) administration by lumbar puncture (LP) every 2 weeks. To qualify for participation in this study, subjects will have participated in Study VTS301 and completed the treatment phase of the study, with assessment by the treating PI in Study VTS301 of continued benefit from treatment with adrabetadex and consensus of the PI in the current study. A completer is defined as a subject who has completed Visit 27/Week 52 or completed at least through Visit 13/Week 24 and required rescue option, and is continuing in Part C of Study VTS301.

Eligible subjects who transition into this study will receive treatment with adrabetadex at the last dose level administered in Study VTS301, administered IT via LP infusion every 2 weeks, for up to a total duration of 3 years or until the investigator considers adrabetadex to be no longer beneficial to the subject, or the adrabetadex development program is discontinued.

This study is intended as open-label treatment for approximately 7 subjects who completed Part B of Study VTS301. This represents subjects who travelled and/or relocated to participate in Study VTS301 and who are willing to continue treatment and observation at a study center that is in closer proximity to where they reside. Any country may serve as a location for an activated study site, including but not limited to Costa Rica, Mexico, and China.

4.2. Study Design Rationale

Adrabetadex is being developed for pediatric use. The typical onset of NPC symptoms is in early childhood. Owing to different clinical presentations and course of disease, NPC is typically categorized as early-infantile onset (less than 2 years of age), late-infantile onset (2 to less than 6 years of age), juvenile onset (6 to less than 15 years of age) and adolescent/adult onset (at least 15 years of age).

Due to the shorter life-span (death is usually within 5 years for early-infantile onset and between 7 and 12 years for late-infantile onset), and the difficulty in making a diagnosis in those subjects with infantile onset forms of NPC, the focus of this drug development program has been for those 4 to 21 years of age with onset of neurologic symptoms before the age of 15. The disease has a relatively slow progression in those with adult onset.

This study is being conducted with the goal of obtaining longitudinal safety and efficacy data; as of the approval of Amendment 2, only safety data will be collected.

4.3. Treatment/Dose Rationale

Subjects in Study VTS301 may have had dosage adjustment based on tolerability. In transition to the current study, the maximum titrated dose established in Study VTS301 will be used as the starting dose. Should tolerability issues occur in the current study, dose reduction is permitted (see [Table 4](#)).

Adrabetadex is administered IT via LP every 2 weeks.

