6.1. Treatment Administration

No new patients can be enrolled in the study.

Eligible subjects who transition into this study will receive treatment with adrabetadex at the last dose level administered in Study VTS301; adrabetadex will be administered IT via LP infusion every 2 weeks, for up to 3 years or until the investigator considers adrabetadex to be no longer beneficial to the subject, or the adrabetadex development program is discontinued. The IT dosing via LP will be conducted by dedicated study personnel in a dedicated room.

Adrabetadex will be administered as an IT slow bolus (1 to 2 minutes, depending on the volume administered) LP injection (maximum rate of administration = 4.5 mL/minute). The volume of the injection is determined by the dose level (see [Table 3](#)). Prior to adrabetadex injection, a volume of cerebrospinal fluid approximately equal to the adrabetadex dose is to be removed. Anesthesia or sedation will be used for the IT dosing procedure, following institutional guidelines and procedures. Subjects will be required, if possible, to lie flat for 30 to 45 minutes following dosing with feet elevated.

Table 3: Adrabetadex Dose, Injection Volume, and Concentration

Dose Level (mg)	Injection Volume (mL)	Concentration (mg/mL)
900	4.5	200
600	3.0	200
400	2.0	200

There is no control product in this study. For additional details, refer to the study manual.

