6.2. Study Treatment Preparation/Handling/Storage/Accountability

Study treatment will be provided by the sponsor or sponsor's representative.

Labeling of the study drug will be in accordance with Good Manufacturing Practice and as required by local and national regulations.

The sponsor (or designee) will ship study drug to the study center. The initial study drug shipment will be shipped after study center activation (ie, all required regulatory documentation has been received by the sponsor and a contract has been executed). Subsequent study drug shipments will be made after study center request for resupply.

Adrabetadex will be provided in appropriately labeled vials (10 mL Type I white glass vial filled with 4.5 mL of adrabetadex, 20 mm FIOLAX stopper, and plastic white flip-off caps coated with FluroTec, or similar vial) formulated as a 200 mg/mL injectable solution. A pharmacist/designee at each study center will be responsible for preparing the assigned dose undiluted (ie, a 900 mg dose will be administered in 4.5 mL, a 600 mg dose will be administered in 3 mL, and a 400 mg dose will be administered in 2 mL). Study drug should be stored between 15°C and 25°C, inclusive.

The investigator or designee will confirm that appropriate temperature control conditions have been maintained during transit for all study treatments received and any discrepancies are reported and resolved prior to study treatment administration.

The study treatment will be maintained in a monitored, environmentally controlled (in accordance with treatment labeling), secure, locked area with restricted access at the study center.

During the study, the study drug will not at any time be handed out to the subjects. The designated study personnel will be responsible for the handling and administration of the study drug during the study.

In accordance with the International Council for Harmonisation (ICH) requirements, at all times the investigator will be able to account for all study drug furnished to the study center. An accountability record will be maintained for this purpose. The investigator must maintain accurate records indicating dates and quantity of study drug received, to whom it was administered (subject-by-subject accounting) and accounts of any study drug accidentally or deliberately destroyed. All unused study drug not involved in immediate subject treatment will be maintained under locked, temperature-controlled storage at the study center.

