6.6. Study Treatment Modification

Subjects who, in the opinion of the investigator, experience a drug-related AE after any IT treatment that is considered clinically relevant and impactful to the subject's function may have their dose of adrabetadex reduced (see [Table 4](#)).

Dose reductions should be considered for subjects who experience a drug-related AE of hearing impairment, asthenia, fatigue, lethargy, marked behavioral disturbance, ataxia, or gait difficulty that:

- Occurs after any IT treatment AND
- Is of moderate or severe intensity AND
- Does not resolve within 48 hours after dosing.

If a subject requires dose reduction due to an AE meeting the above criteria, and if a subject continues to experience an AE of note after dose reduction, the subject's dose may be reduced as described in [Table 4](#).

Table 4: Adrabetadex Dose Reductions Due to Drug-Related Adverse Events

Dose Level (mg) at Time of Adverse Event	Reduced Dose (mg):
900	600
600	400
400	Dose may only be reduced after discussion with MM on a case-by-case basis, with a lower limit of 200 mg.

The AE that led to the dose reduction must be fully documented.

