8.4. Treatment Overdose

For this study, any dose greater than the dose to be administered per protocol, within a 24 (± 1) hour period, will be considered an overdose.

The effects of an overdose of adrabetadex are not known. In the event of overdose, subjects should be observed and appropriate supportive treatment should be given. There is no known specific treatment in case of overdose.

The highest dose of adrabetadex administered in humans is 1800 mg, as described in the Investigator's Brochure. Side effects seen at this dose were similar to those seen at other doses, with increased intensity, severity, and duration.

In the event of an overdose, the investigator or designee should:

- Contact the MM immediately.
- Closely monitor the subject for any AE/SAE and laboratory abnormalities should be recorded.
- Document the quantity of the excess dose, as well as the duration of the overdose.

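### Section 4.3 sets the starting dose by an undefined maximum titrated dose while five other places use the dose at VTS301 exit; the two rules can differ, and the overdose definition depends on which applies

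*Combined protocol and SAP*

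**What the plan says.** Six places in the protocol state the starting dose.

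- **Section 6.1** (treatment administration): "Eligible subjects who transition into this study will receive treatment with adrabetadex at the last dose level administered in Study VTS301". Section 4.1 and the overall design part of the Synopsis give the same rule: subjects "will receive treatment with adrabetadex at the last dose level administered in Study VTS301".
- **Section 2.2** expresses an exit-dose rule in other words: "Subjects will enter this study at the same dose and regimen they were taking upon exiting Study VTS301". The Synopsis rationale repeats this.
- **Section 4.3** (dose rationale) is the exception: "In transition to the current study, the maximum titrated dose established in Study VTS301 will be used as the starting dose". The sentence just before it reads: "Subjects in Study VTS301 may have had dosage adjustment based on tolerability".

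The protocol does not define maximum titrated dose, and it does not give the VTS301 rules for titration, reduction or re-escalation.

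Two other sections refer to a protocol dose or may do so. Section 8.4 counts as an overdose "any dose greater than the dose to be administered per protocol", within a window of about 24 hours, and requires immediate contact with the medical monitor. Section 6.4 says that the amount given is recorded and that compliance will be calculated, but names no reference dose.

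**The concern.** A last dose and a maximum dose can part company when a dose has been lowered, and Section 4.3 itself says that VTS301 doses may have been adjusted for tolerability. The ambiguity therefore falls on subjects who had tolerability problems, in a study whose only objective is long-term safety and tolerability.

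What is at stake is how doses are classified. If two starting doses can both claim to be the protocol dose, then whether an injection was an overdose or a deviation depends on which section is read. Compliance is affected in the same way if it is calculated against the protocol dose. The ambiguity also reaches past the first injection. The protocol describes dose reductions (Section 6.6, Table 4) but no increases, so the starting dose remains the reference until a reduction is made.

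Dose relative to exit dose also matters for reading the adverse events. Section 2.3 reports dose-dependent hearing impairment in animal models and says higher doses may bring further impairment, and hearing impairment is the adverse event of special interest (Section 10.3.5).

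**Working it through.** There is no planned figure to reproduce. The sample size of about 7 is set by availability (Section 9.1). The check is a comparison of texts, with dose ratios as illustration only.

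**Step 1: the rules.** Rule A (Sections 2.2, 4.1 and 6.1, and two places in the Synopsis) is the dose at VTS301 exit. Rule B (Section 4.3) is the maximum titrated dose.

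**Step 2: two readings of Rule B.**
- B1: the highest dose reached at any time in VTS301.
- B2: the dose settled on after any adjustment for tolerability.

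The sentence before Rule B, on tolerability adjustment, allows B2. The word maximum, and the following sentence permitting reduction if tolerability problems occur in the current study, fit B1 but do not prove it. The text does not decide between them.

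**Step 3: dose levels.** Table 3 gives 900, 600 and 400 mg as 4.5, 3.0 and 2.0 mL, and Section 6.2 agrees ("a 900 mg dose will be administered in 4.5 mL, a 600 mg dose will be administered in 3 mL"). Assumption: VTS301 used the same three levels. The documents do not say so. Table 4 also allows a case-by-case reduction in the present study ("Dose may only be reduced after discussion with MM on a case-by-case basis, with a lower limit of 200 mg"). That level is left out because nothing links it to VTS301.

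**Step 4: compare.** Ratio = dose under B1 / dose under A.

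| VTS301 dose history | Rule A | B1 | B2 | B1 / A |
|---|---|---|---|---|
| 900 mg, never reduced | 900 | 900 | 900 | 900/900 = 1.0 |
| 900 to 600 mg, still 600 at exit | 600 | 900 | 600 | 900/600 = 1.5 |
| 600 to 400 mg, still 400 at exit | 400 | 600 | 400 | 600/400 = 1.5 |
| 900 to 400 mg, still 400 at exit | 400 | 900 | 400 | 900/400 = 2.25 |
| 900 to 600 mg, back to 900 before exit | 900 | 900 | 900 | 900/900 = 1.0 |

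The B2 column assumes that the settled dose was still in use at exit; A and B2 then agree in every row. A and B1 differ only in the three rows where the subject left VTS301 on a reduced dose.

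**Step 5: carry into Section 8.4.** Take the second row and suppose 900 mg is given. Under Rule B read as B1, the protocol dose is 900 mg and the injection is per protocol. Under Rule A, the protocol dose is 600 mg, 900 mg exceeds it, and the injection meets the overdose definition. If 600 mg is given instead, it is per protocol under A and below the protocol dose under B1.

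**Step 6: how many subjects.** The number still on a reduced dose at VTS301 exit is not given. It could be anything from none to all of the roughly 7.

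**The case against.** The strongest reply is that 4.3 is loosely worded and does not conflict with the rest. Coming straight after a sentence on tolerability adjustment, the phrase can be taken as the dose established once adjustment was complete, and on that reading all six places normally agree. The other five, including the administration section, use the exit dose. Enrolment is closed (Section 5), and treatment ends by 20 October 2021 (Section 7.1), so rewording 4.3 changes no future starting dose.

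Much of this stands. The harmless reading is possible, and the reach is now mainly retrospective. But the text does not state that reading, and counting places does not settle the meaning of an undefined dose term in a multinational study. Existing subjects could still be dosed until the cut-off date, and overdoses and deviations must still be classified for the report.

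The reply is also right against three stronger readings that a reader might infer:

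- *Every subject reduced in VTS301 gets a different dose under 4.3.* This requires reading maximum as highest reached, and it fails for anyone re-escalated to that dose before exit.
- *Subjects were restarted on a dose they had not tolerated.* Nothing in the documents shows that this happened.
- *The safety data cannot be read by dose until the rule is settled.* Section 6.4 has the amount given recorded, and reading events by dose needs the dose given, not the dose prescribed. What stays unsettled is classification against the protocol dose.

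**Conclusion.** The inconsistency is real and lies in current operative text. Section 4.3 uses an undefined term that can conflict with Sections 2.2, 4.1 and 6.1 and both Synopsis statements. The doses differ only if the term means the highest dose reached, and only for a subject still on a reduced dose at VTS301 exit.

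Where they differ, the factor is 1.5 or 2.25, provided VTS301 used the 900, 600 and 400 mg levels. The number affected cannot be derived and may be zero.

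The firm consequence is for the overdose definition in 8.4, and with it the classification of deviations. An effect on compliance is conditional, because 6.4 does not state its reference dose. With enrolment closed, the point concerns classification and interpretation of the safety data. It is worth correcting because safety is the sole objective and the correction is small.

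**What to change.** **Protocol.** The sponsor should define maximum titrated dose and reconcile Section 4.3 with Sections 2.2, 4.1 and 6.1 and the Synopsis. Which rule is right is for the sponsor and its clinical team; none is proposed here. The reference dose for the compliance calculation in 6.4 should be stated at the same time. Section 10.1.1 requires an amendment for any change in the study plan, so the text could be corrected with the next one.

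**Report.** No amendment is needed for the following:

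- List for each subject the last VTS301 dose, the highest VTS301 dose and the actual VTS302 starting dose.
- Flag any starting dose that differs from either definition, in either direction, so that neither rule is treated as the reference by default.
- Add the actual dose at onset to the adverse event listings already planned in Section 9.3.2, which does not mention dose.
- State which rule was used to classify overdoses and deviations.

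The cost is a short text change plus one listing and one added column for about 7 subjects. Doses in the present study are recorded under 6.4. The VTS301 doses should come from the lifetime NPC treatment history required by Section 6.5 or, failing that, from the VTS301 data.
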